Following the initial 7-day active exogenous progesterone treatment period, participants will return for a laboratory-based stressor a session. The primary study outcomes of interest in Aim 2 are the differential craving, stress and anxiety responses of progesterone- vs. placebo-treated participants in response to the psychosocial stressor (TSST). Hypothesis 1: Compared to placebo, progesterone will attenuate stress cue reactivity during a human laboratory stress paradigm among women but not men with CUD. Immediately prior to and following the TSST (baseline, +0, +5, +30, and +60 minutes), self-reported measures of stress and craving will be collected. To assess the effect of exogenous progesterone administration on stress and craving response to the TSST, linear mixed effects models will be developed to assess differential treatment responses over time. The primary independent variable of interest will be randomized treatment assignment (progesterone vs. placebo). In addition to overall treatment differences, least squares means and associated standard errors will be used for post-hoc

comparisons between treatment groups at each post-cue time point. Additionally, sex will be added to the model and differential effect of progesterone will be assessed using an interaction term. When significant, stratified treatment effects will be compared and presented across females and males.

Aim 3: Evaluate stress, sex, and endogenous progesterone influences on cannabis craving and use.

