C.2.d.3. Power and Sample Size (complete sample size estimation is provided in Biostatistics Resource Core). In the proposed study, cue response and withdrawal data will be tested using GLMMs (assuming a Gaussian distribution) and the study will be powered to sufficiently address the smallest effect sizes determined to be clinically meaningful for the study hypothesis. Fox and colleagues (2013) examined exogenous progesterone and placebo administration on cue response in 42 cocaine dependent participants. Results indicated that female participants receiving placebo experienced larger negative emotion scores in response to stress-related cues than male participants on placebo ($\Delta=4.7$; $SD_P=3.4$; between sex Cohen's $d > 1.0$, $p < 0.01$). Fox and colleagues also found that administration of exogenous progesterone reduced stress-cue related negative emotions significantly in women ($\Delta=2.4$; $SD_P=3.4$, $d=0.71$) but not in men ($\Delta=-0.7$; $SD_P=3.3$ $d=-0.2$; treatment x sex interaction $\Delta=3.1$; $SD_P=4.7$, $d=0.67$). Assuming a similar response profile between treatment assignments and sex as above, a sample size of 64 participants (32 women, 32 men to each treatment assignment) randomized to the progesterone vs. placebo groups would guarantee 80% power with a type 1 error rate of 5% to detect the least effect size of $d=0.67$ in the stress reduction treatment x sex interaction (total $n=128$) during the 7-day, active treatment CREMA assessment period. Although the proposed study is of relatively short duration, we do anticipate 10% attrition between randomization and the end of the 1-week active treatment period and laboratory session. Thus, inflating the necessary sample size to 70 participants (35 men and 35 women), a total of $n=140$ randomized participants will be needed. Due to app issues at the beginning of the study, some initial data is unusable, so we will randomize 90 men. Additionally, data from our recently completed SCOR project, which examined daily salivary progesterone levels and cigarette smoking behavior for 14 consecutive days in untreated female participants, indicated that increased levels of daily progesterone within participant was associated with decreased cigarettes smoked per day ($\beta=-0.32$; $SE=0.14$; $p < 0.05$). To detect a similar correlation ($\beta=\pm 0.32$; $SD=1.0$) between daily progesterone levels and associated daily use metrics in the proposed study, the randomized sample of 70 women (62 with available follow up data), with 14 days of follow up use data, and with an autocorrelation of 0.9, would provide 80% power. The proposed sample size of **n=160** randomized

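### Aim 2 hypothesises an effect in women but not men, yet does not name the treatment-by-sex interaction as its test and presents sex-specific effects only when significant

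*Combined protocol and SAP*

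**What the plan says.** In C.2.d.1, Aim 2, the only hypothesis is that "progesterone will attenuate stress cue reactivity during a human laboratory stress paradigm among women but not men with CUD". The analysis then runs in this order:

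- A linear mixed model of the TSST responses over time, where "The primary independent variable of interest will be randomized treatment assignment (progesterone vs. placebo").
- Estimates of the treatment difference: "In addition to overall treatment differences, least squares means and associated standard errors will be used for post-hoc" comparisons at the separate time points after the stressor.
- A further step: "Additionally, sex will be added to the model and differential effect of progesterone will be assessed using an interaction term".
- A condition on output: "When significant, stratified treatment effects will be compared and presented across females and males". The text does not say which test must be significant or at what level. The preceding sentence makes the interaction the natural candidate.

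C.2.d.3 takes its effect sizes from a cited study of cocaine-dependent participants, which found that "administration of exogenous progesterone reduced stress-cue related negative emotions significantly in women" (difference 2.4, SD 3.4) but not in men (difference -0.7, SD 3.3). It derives 80% power for d=0.67 "in the stress reduction treatment x sex interaction", for the 7-day CREMA period, which is Aim 1. It closes by claiming at least 80% for the sex and treatment comparisons of the primary aims, without listing them. It gives no effect size or SD for the TSST. The section also notes that the "complete sample size estimation is provided in Biostatistics Resource Core", which is not among the documents reviewed.

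**The concern.** A hypothesis of an effect in one sex and not the other is a statement about the treatment-by-sex interaction, with the effect in women as its main estimate. The Aim 2 text gives the primary label to treatment and leaves the interaction as an addition. It is then unclear which result decides the hypothesis.

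The output condition matters more. Followed as written, it lets a p-value decide whether the estimate the hypothesis is about appears at all. A trial with a clear effect in women and an interaction just short of significance would present only the treatment difference, and readers could not see the women's estimate or its precision. Later evidence synthesis would receive the women's effect only from the trials in which the interaction happened to be significant.

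**Working it through.** **The plan's own figure.** C.2.d.3 states 80% power for the interaction with 32 per sex-by-treatment cell and d=0.67. The SD of the interaction contrast is sqrt(3.4² + 3.3²) = 4.74, matching the stated 4.7, and 3.1/4.7 = 0.66. With a normal approximation, two-sided 5% and one value per participant, power = Φ(0.67 × sqrt(32/2) − 1.96) = Φ(0.72) = 76%, or 75% with 3.1/4.7. So 80% is not reproduced by the simple formula; 35 per cell would give it with d=0.67. This does not prove an error. The planned model uses repeated measures, the correlation used for this calculation is not given, and the full calculation is in the Biostatistics Resource Core.

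**Inputs for the output rule.** Effects and SDs are those of C.2.d.3. Randomised numbers are 70 women and 90 men (C.2.a). The 10% attrition in C.2.d.3 leaves 63 and 81. I assume 1:1 allocation within sex, one summary value per participant, two-sided 5%, and that the condition refers to the interaction.

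**Standard errors.**
- Women: sqrt(4 × 3.4²/63) = 0.857
- Men: sqrt(4 × 3.3²/81) = 0.733
- Interaction: sqrt(0.857² + 0.733²) = 1.128

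**Power (noncentral t).**
- Women's own test: 2.4/0.857 = 2.80, power 79%.
- Interaction, men at -0.7: 3.1/1.128 = 2.75, power 78%.
- Interaction, men at zero: 2.4/1.128 = 2.13, power 56%.

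**What the rule withholds.** The sex-specific effects are withheld whenever the interaction is not significant: 100 − 78 = 22% of trials, or 100 − 56 = 44% with men at zero. The women's estimate and the interaction share data (correlation 0.857/1.128 = 0.76), so the joint event was simulated with 400,000 trials:

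| Men's true effect | Sex-specific effects withheld | Women's effect significant but unpresented |
|---|---|---|
| -0.7 (C.2.d.3) | 22% | 9% |
| 0 | 44% | 25% |

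**Sensitivity.** Adjusting for a baseline value with correlation r multiplies the SDs by sqrt(1 − r²). With r = 0.5 and 0.7 (assumed, not in the documents), a significant women's effect goes unpresented in about 6% and 2% of trials with men at -0.7, and in about 22% and 13% with men at zero.

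**Selection effect.** With men at -0.7, the women's effect averages 2.65 when the interaction is significant (+10% over 2.4). Selecting on the women's own test gives 2.71 (+13%). With men at zero, selection on the interaction gives 2.85 (+19%).

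**The case against.** The strongest reply is that the right test is already in the plan. The interaction term is stated for Aim 2, C.2.d.3 sizes the trial on a treatment-by-sex interaction, and its attrition allowance runs to the laboratory session. C.2.e (iv) says men are included to find effects unique to one sex or shared by both, so estimating a treatment effect too is deliberate. Looking at subgroup effects only after a significant interaction is common practice, and a significant effect in women without an interaction would not establish the women-but-not-men claim. All of this stands. It reduces the first part of the point to naming the test. It does not rescue the output condition: the women's effect is the pre-stated hypothesis rather than an unplanned subgroup, and an estimate with its interval is informative whether or not the interaction is significant.

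A reader might infer three stronger things that the documents do not support:

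- *That a both-sexes effect is the declared test of the hypothesis.* The word overall is set against comparisons at separate time points, so it refers to time. A model without a sex term would pool the sexes, but the text does not call that result the test.
- *That the closing 80% claim is false for Aim 2.* The claim does not name its contrasts. With one value per participant, power for the effect pooled over sexes is 22-32% at 63/81 with men at -0.7, but it reaches 84-88% with men at zero and r = 0.7. The interaction itself has about 73-74% at 63-64 per sex, and 56-61% at 63/81 to 70/90 with men at zero. With no TSST variance given and the full calculation unseen, the documents do not settle which Aim 2 contrasts reach 80%.
- *That the rule distorts the women's estimate unusually.* At the plan's own effects the inflation is no worse than ordinary significance filtering.

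**Conclusion.** The point holds for labelling and for reporting. Aim 2 does not say that the treatment-by-sex interaction decides its hypothesis, and it makes presentation of the women's effect conditional on significance. At the plan's own effects this withholds the sex-specific results in about 22% of trials and hides a significant women's effect in about 9%. With no effect in men, which is the literal hypothesis, the figures are about 44% and 25%. With a useful baseline covariate, the share with a hidden significant effect falls to 2-6%, or 13-22% with men at zero.

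These sizes borrow negative-emotion effects from cocaine users, use one value per participant, count all 81 completing men as usable, and read the condition as referring to the interaction. The case for unconditional reporting does not depend on them. The closing power statement is a lesser matter of clarity: its 80% for a treatment comparison is derived only for the interaction in the CREMA week.

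**What to change.** In C.2.d.1, Aim 2:

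1. Include treatment by sex (by time) in the mixed model from the start, and name it as the test of Hypothesis 1.
2. Replace the conditional sentence with a commitment to report the treatment effect and its confidence interval in women and in men, whatever the interaction p-value.
3. Keep the treatment effect pooled over sexes as a secondary contrast.

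In C.2.d.3, have the closing sentence name the contrasts and the outcome that its 80% covers. Take any Aim 2 power figures from the planned TSST repeated-measures model, with its assumed variance and correlation stated, and reconcile both sections with the Biostatistics Resource Core plan.

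The cost is wording, plus a power calculation if Aim 2 figures are to be quoted. No new data or participants are needed.

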b. Substance-Related Instruments. Time Line Follow-back: The Time Line Follow-back (TLFB; Sobell & Sobell, 1992) is a calendar-based instrument designed to assess daily substance consumption. Cannabis use will be recorded in times used per day as well as quantity (e.g., grams, number of blunts/joints) in order to standardize for different types of cannabis use. **Urine Drug Screening:** Qualitative drug screens will be performed using the One Step Multi-Drug Test Dip Card (DrugconfirmTM), a lateral flow chromatographic immunoassay for the qualitative detection of drug or drug metabolite in the urine at the following cutoffs (ng/ml): cocaine (300), amphetamines (1000), THC (50), opiates (2000), and benzodiazepines (300). In addition, quantitative urine cannabinoid drug screens will be performed using the AXSSYM® system from Abbott Laboratories. This assay is semi-quantitative with a detection cut-off value of 30.00 ng/ml (Abbott AXSSYM® System package insert). Urine creatinine will also be obtained, as creatinine normalization has been proposed as a method to differentiate new cannabis use from residual drug excretion (Huestis & Cone, 1998; Schwilke et al, 2011). Results will be used to ascertain abstinence prior to study procedures, cannabinoid levels, and to substantiate self-reports of all substance use. **Breathalyzer** (AlcoSensor III, Intoximeters, Inc., St. Louis): To ascertain abstinence from alcohol prior to study visits, participants will have their breath sampled for the presence of alcohol (Alco-Sensor III, Intoximeters Inc., St. Louis, MO). **Inventory of Drug-Taking Situations (IDTS)** (Annis et al., 1997): This instrument measures typical drug using situations based on Marlatt and Gordon's (1985) eight category taxonomy. This instrument contains eight subscales mapping frequency of use in eight distinct types of situations including use during negative situations (unpleasant emotions) and positive situations (social situations). Although initially developed to assess alcohol use, this scale has been modified for use with drug abusers and has demonstrated sensitivity to sex differences (Ross et al., 1994).

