c. Remote screening visit alternative. Patients may also complete the initial visit remotely if warranted. In this case, subjects will be electronically consented through a secure platform such as Doxy.me or Redcap. The informed consent will be emailed to the participant prior to the video call. The patient will have the opportunity to ask questions on the call and will electronically sign the document. A signed copy will be emailed to the participant. The M.I.N.I interview and medical history then be conducted, also via Doxy.me. If clinically indicated, patients may have a physical exam the UDS visit. To date, no patients have been excluded due to physical exam findings. Patients will be advised to find a private location during these procedures to protect privacy and confidentiality. Patients will be sent survey links to complete self-report questionnaires.

d. Blood draws: In order to investigate the impact of moderate to heavy cannabis use and menstrual cycle on the endocannabinoid system, blood will be taken at Days 1, 8 and 22.

C.2.c.3. Progesterone Administration Procedures (Study Days 1-7). Following completion of screening procedures, participants will be scheduled to come to the clinic for training on CREMA and saliva (progesterone) collection procedures. The TLFB calendar will be completed. For female participants, menstrual history data will be used to schedule this session in the early follicular phase to standardize progesterone (or placebo) administration. During the early follicular phase, defined as the first 7 days after the onset of menses, ovarian hormones are low and largely invariant (approximately <1.1 ng/ml for progesterone and <85 pg/ml for estradiol; Chabbert-Buffet et al., 1998). This is critical for two reasons; first, to minimize the interaction between endogenous and exogenous sex hormones, and second, to achieve consistency between males and females as progesterone levels in men are steady and similar to levels observed in women during most of the follicular phase (Zumoff et al., 1990). At this visit, a urine sample will be collected to assess baseline cannabinoid level for purposes of cannabis abstinence verification (described below). Participants will be instructed to refrain from cannabis use during this study period.

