Participants will be provided with a seven-day supply of progesterone or placebo. Randomization to treatment will be done by the MUSC Investigational Drug Service (IDS). Dosing will begin in the evening on study day 1. On study days 2-7 participants will take medication at home in the morning and evening, and on day 8 the final dose will be taken at in the morning prior to completion of the laboratory stress task (described below). Progesterone and matching placebo capsules will be prepared and dispensed by the MUSC IDS. Previous studies (Fox et al., 2013; Sofuoglu et al., 2001; 2011) have used twice daily administration of 200mg progesterone during the early follicular phase to achieve stable levels of progesterone comparable to normal luteal phase levels (2-20 ng/ml). Safety and tolerability of micronized progesterone have been established in numerous studies with nicotine (Sofuoglu et al., 2001; 2011) and cocaine (Evans & Foltin, 2006; Fox et al., 2013; Reed et al., 2011 Sofuoglu et al., 2002; 2004) dependent individuals.

c. Cannabis Abstinence Verification. Cannabis abstinence will be assessed using self-report, saliva drug testing, and cannabinoid levels. Self-report will be collected at study visits using the TLFB as well as collected daily through mobile surveys or “morning reports” completed via mobile electronic device. Participants will be trained to self-administer saliva drug screening (Oratect FDA approved saliva test.). This test is able to detect THC in saliva for up to 14 hours. Participants will be instructed to complete two saliva drug tests daily using the RedCap video upload procedure described below under *Medication Adherence/Drug Test Monitoring*. A test will be completed in the office on Day 1 so patients can practice the procedure. Cannabinoid levels will also be assessed using urine toxicology collected on Study Days 8 and 22. Creatinine-corrected cannabinoid levels will be compared from Day 1 to Day 8 to confirm abstinence during the study period. Our group has recently published on the need for utilization of multiple methods to determine cannabis abstinence (Baker et al., in press). Contingency management (monetary compensation) procedures will be incorporated to promote abstinence (described below).

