d. Medication Adherence/Drug Test Monitoring. Participants will record themselves taking their morning and evening medication doses as well as completing the twice daily saliva drug test swab procedure. Photos of the completed saliva test will be uploaded. A survey link will be sent to the participant’s (or study provided) cell phone via CREMA app alert twice daily. Video capture will occur as part of a RedCap survey. As discussed in the Preliminary Data section, we have previously utilized this technology successfully for both medication adherence monitoring and to remotely assess substance use. To encourage compliance with study procedures, participants will receive \$10 for completion of each medication adherence video. Participants will receive an additional \$30 for each saliva drug screen that is negative for all drugs of abuse. A similar compensation schedule was effective in our pilot progesterone study. Study staff will call participants twice during this week to see if they are having any difficulties with the procedures or side effects from the medication. Study staff will also text abstinence reminders to patients whose saliva tests positive for drugs of abuse.

e. CREMA Assessment. Cue Reactivity Ecological Momentary Assessment (CREMA; Warthen & Tiffany, 2009; Wray, Godleski, & Tiffany, 2011; Wray et al., 2015) is a cue reactivity assessment in which photographic stimuli are presented multiple times per day on a mobile electronic device (i.e iPhone). In cases where participants do not have a smart phone or do not wish to use their own device for the purposes of the study, a phone will be provided. Participants will be instructed to keep their phone with them at all times. Phones will be password protected to prevent access to the study assessments and surveys by anyone other than the participant. Auditory alarms will alert participants to complete three, randomly scheduled CREMA sessions per day (session duration = 3-4 minutes). Alarms will be distributed over a 12-hour period, divided into three, 4-hour blocks with a minimum time of 30 minutes between alarms/CREMA sessions. In order to accommodate varying participant wake-sleep schedules, participants will be able to choose the 12-hour period during which they will be prompted and this may vary from weekdays to weekends. There will be two types of picture cues that differ based on content:

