C.2.c.4. Laboratory Stress Induction Session (Day 8). Following the one-week period of progesterone or placebo administration, participants will return to the study clinic to complete a laboratory stress task (Trier Social Stress Test, TSST). Data from this task will be used to complement the “real world” stress reactivity data collected via CREMA. If participants become unable to attend the session on Day 8, they may be re-scheduled for the following day. However, participants will not be re-scheduled after Day 9.

a. Session Preparation. Participants will be instructed to arrive at 11:00am on the day of the TSST, and to avoid caffeinated beverages on the test day since caffeine can inflate reactivity to the stressor. If the individual is nicotine-dependent, (s)he will be provided with a nicotine patch throughout their study visit. Upon arrival, the participant will be breathalyzed and will provide urine and saliva samples, which will be tested for the presence of marijuana, cocaine, opiates, barbiturates, benzodiazepines, and stimulants. The urine sample will also be quantitatively analyzed for cannabinoids and creatinine to confirm past week cannabis abstinence. At 10:30am, saliva (progesterone) will be collected, and a blood pressure cuff will be placed on the participant’s arm. Two baseline assessments of subjective, hormonal (cortisol; see Assessments below for details), and physiologic measures (blood pressure and heart rate) will be collected, one at 11:40am and the second at 11:55am.

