Endogenous progesterone levels (via saliva samples) will be obtained daily for two weeks following the completion of the active medication portion of the study. Daily progesterone levels will be assessed for associations with stress and craving responses to stress vs. neutral CREMA cues. *Hypothesis 1: Among women, higher daily levels or increasing endogenous progesterone will be associated with decreased cannabis use.* To evaluate this hypothesis, a multilevel generalized linear mixed effects models with repeated measures (GLMMs) will be developed using CREMA session response data from the 2-week follow up period. Statistical models will include day and subject level data, measured longitudinally. Daily salivary progesterone levels will be included as the primary independent predictor cannabis use. Relevant interactions will be assessed in all models. Additionally, increases in progesterone during the early luteal phase of each female participant's cycle will be evaluated; models will include dynamic changes in progesterone (between day rates of change) as a predictor of attenuated cannabis use. *Exploratory Hypothesis 2: High stress will be associated with cannabis craving and return to cannabis use in women more than men.* Time from the laboratory session to return to cannabis use (latency, in days) will be computed for all study participants. Kaplan-Meier estimates and log-rank tests will be used to assess initial relationships between measures of stress reactivity during the TSST (e.g., subjective stress, anxiety, BP, HR, cortisol) and relapse/latency while Cox proportional hazards models will be developed to assess the differential latency to use across sex for each stress reactivity measure during the TSST (using an appropriate interaction term; e.g. Peak TSST stress response x sex). Additionally, daily stress and craving responses to CREMA picture cues will serve as time-dependent covariates in latency models to assess the influence of recent stress and craving responses on relapse/latency.

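### Latency to return to cannabis use is computed for all participants, including any still using at Day 8, so the exploratory relapse risk set is wrong and the stress-by-sex estimate can be biased either way

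*Combined protocol and SAP*

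**What the plan says.** The hypothesis in C.2.d.1, Aim 3 is: "Exploratory Hypothesis 2: High stress will be associated with cannabis craving and return to cannabis use in women more than men". The outcome rule is: "Time from the laboratory session to return to cannabis use (latency, in days) will be computed for all study participants". Kaplan-Meier and log-rank analyses follow, then Cox models of sex differences for each TSST reactivity measure ("using an appropriate interaction term; e.g. Peak TSST stress response x sex"). Daily CREMA stress and craving responses also enter the latency models as time-dependent covariates.

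On abstinence before the session, the protocol says:

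- C.2.c.3: "Participants will be instructed to refrain from cannabis use during this study period".
- C.2.c.3.c: "Creatinine-corrected cannabinoid levels will be compared from Day 1 to Day 8 to confirm abstinence during the study period". Self-report and twice-daily saliva tests are collected as well.
- C.2.c.3.d: negative saliva tests are paid for. For positive ones, "Study staff will also text abstinence reminders to patients whose saliva tests positive for drugs of abuse".
- C.2.c.4.a, on arrival for the TSST: "The urine sample will also be quantitatively analyzed for cannabinoids and creatinine to confirm past week cannabis abstinence".
- C.2.c.2.b, on urine testing: "Results will be used to ascertain abstinence prior to study procedures, cannabinoid levels, and to substantiate self-reports of all substance use".

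None of these sections gives a threshold for abstinence, makes abstinence a condition for the TSST, or says how a participant whose abstinence is not confirmed enters the latency analysis. C.2.d.1 and C.2.d.2 refer to a fuller plan in the Biostatistics Resource Core, which is not among the documents.

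**The concern.** A time-to-event analysis needs everyone in the risk set to be able to have the event at time zero. The event here is going back to cannabis. Someone still using when the clock starts cannot go back to it, and whatever latency is recorded for that person (presumably about a day) describes continued use, not relapse after the stressor.

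Such people may well be present. Participants are not seeking treatment (C.2.a), use at least five times a week at entry (C.2.c.2), and appear to stay in the study after a positive saliva test. By the protocol's own account, withdrawal raises anxiety and craving (C.2.e), so a continuing user's TSST response may also be measured in a different state from an abstainer's.

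At stake is the stress-by-sex interaction on relapse, which is the content of this hypothesis. If continued use in Days 1 to 7 is related to stress or to sex, the analysis mixes the causes of not stopping with the causes of relapse.

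**Working it through.** The plan gives no event rate, hazard ratio, abstinence rate or power for the latency analysis, so it has no figure to reproduce. The check has two parts.

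**1. Can the rule be applied as written?** C.2.d.3 anticipates 10% attrition by the laboratory session: 160 × 0.10 = 16 of the 160 randomised. With no session these participants have no time origin, so the rule cannot cover everyone even on its own terms. Among attenders, those still using have a time origin but are not at risk of the event.

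**2. What does keeping continuing users do to the interaction?** This was simulated.

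Inputs from the documents: 62 women with follow-up data (C.2.d.3); 90 × 0.9 = 81 men; 14 days of follow-up (C.2.c.5); latency in whole days (C.2.d.1).

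Assumptions, none from the documents. Let s be standardised TSST reactivity and x = 1 for women:

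- Daily hazard of return among abstainers: 0.12 × exp(0.3s + b·s·x + 0.2x), with b = 0.50 (hazard ratio 1.65) or b = 0. For a man of average reactivity the 14-day return probability is 1 − exp(−0.12 × 14) = 81%.
- Non-abstainers are given an event on day 1.
- The non-abstinent share f (its value at average reactivity) is 10, 20, 30 or 50%. Non-abstinence has probability p, with three patterns: **A**, unrelated to s, p = f; **B**, logit p = logit f + 0.3s + 0.9s·x (rises with stress, more in women); **C**, logit p = logit f − 0.9s·x (falls with stress in women).

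A Cox model with s, x and s·x and Efron ties was fitted 600 times per setting (400 for b = 0). Cells show the mean estimate of b and, in brackets, the two-sided 5% rejection rate.

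| Pattern, true b | f | All kept | Abstainers only |
|---|---|---|---|
| A, 0.50 | 10% | 0.430 (57%) | 0.505 (65%) |
| | 20% | 0.352 (44%) | 0.495 (59%) |
| | 30% | 0.294 (34%) | 0.502 (51%) |
| | 50% | 0.183 (15%) | 0.502 (41%) |
| B, 0.50 | 10% | 0.524 (76%) | 0.508 (57%) |
| | 20% | 0.492 (69%) | 0.526 (53%) |
| | 30% | 0.465 (69%) | 0.509 (44%) |
| | 50% | 0.404 (59%) | 0.549 (35%) |
| C, 0.50 | 10% | 0.252 (26%) | 0.478 (57%) |
| | 20% | 0.122 (10%) | 0.498 (55%) |
| | 30% | 0.008 (5%) | 0.484 (45%) |
| | 50% | −0.111 (10%) | 0.513 (40%) |
| B, 0 | 10% | 0.123 (8%) | 0.002 (5%) |
| | 20% | 0.191 (18%) | −0.015 (4%) |
| | 30% | 0.198 (17%) | −0.007 (6%) |
| | 50% | 0.199 (18%) | 0.019 (7%) |

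With nobody non-abstinent the estimate is 0.504 and power 68%. With pattern A and b = 0, both analyses centre on zero and reject in 4 to 7% of runs. The Monte Carlo standard error of a 5% rejection rate over 400 runs is √(0.05 × 0.95/400) = 1.1 percentage points. The 8% at f = 10% is therefore only marginally raised, while 17 to 18% is clearly raised.

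In A the interaction is diluted. In B with a true effect, the errors roughly offset up to 20%. In C the estimate is badly attenuated and can change sign. In B with no true effect, an interaction is manufactured.

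**The case against.** Several points on the other side carry weight.

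- *The full plan is elsewhere.* The Biostatistics Resource Core document may contain a rule for continuing users. That cannot be ruled out, but the supplied text says all participants and should not be left to contradict it.
- *The phrase may only mean both sexes.* Hypothesis 1 of the same aim is confined to women, so the wording may simply bring men in. That is a fair reading of intent, but no exclusion follows from it.
- *Restriction has its own price.* It conditions on a post-randomisation state that may depend on stress, sex and treatment. This stands. The simulation includes no unmeasured common cause of early use and later relapse, so its recovery of about 0.50 does not show that restriction is free of selection effects.

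A reader might also draw stronger conclusions that the documents do not support.

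- *That the effect is necessarily diluted.* This needs non-abstinence to be unrelated to reactivity. The documents do not say so, and their premise that stress drives use, particularly in women (A.3, A.8), makes other patterns plausible.
- *That restriction always gains power.* It does in A. In B with a true effect, power is 59 to 76% with everyone kept and 35 to 57% after restriction, although part of the former is artefact, as the b = 0 rows show.
- *That the protocol expects many participants not to stop.* The text reminder is a contingency for any drug of abuse, negative tests are paid for, and a pilot of 8 (C.1.c) reported being able to recruit and retain people willing to abstain. No rate is given.
- *That anyone who used in Days 1 to 7 should be removed.* A participant who lapsed on Day 3 and then stopped is properly at risk of returning to use.

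**Conclusion.** The concern holds for the risk set. As written, the latency analysis includes anyone still using at Day 8 as if at risk of relapse, and nominally includes people with no session. This follows from the text and needs no assumed rate.

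The size and sign of the bias are not determined by the documents. The simulated range runs from a true 0.50 estimated at 0.43 to 0.18 (pattern A), through near-offsetting errors, to a null interaction estimated at 0.12 to 0.20. It rests on the assumed hazards, the non-abstinent shares and the day-1 event given to continuing users.

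The hypothesis is labelled exploratory. Aims 1 and 2 and Aim 3 Hypothesis 1 do not use latency and are unaffected. The text should be corrected, but the trial's main conclusions do not depend on it.

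**What to change.** In C.2.d.1, Aim 3, Exploratory Hypothesis 2:

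1. Make the main latency set those who attended the laboratory session and were abstinent at that point (Day 8, or Day 9 if rescheduled). Judge this from the saliva tests, TLFB and daily reports, and creatinine-corrected urine already collected. State in advance how abstinence is classified and which measure prevails if they disagree. The Day 1 to Day 8 urine comparison reflects the whole week, so it should not by itself remove someone who lapsed early and then stopped.
2. Define return to use, the time origin and censoring at the end of follow-up.
3. Label the result as relapse among those who had stopped.
4. Keep all session attenders as a sensitivity analysis, stating the latency assigned to continuing users.
5. Report the number of continuing users by sex, arm and TSST reactivity, so that readers can judge which bias pattern is plausible.

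This is an analysis classification only and changes nothing in how participants are managed. It needs a short paragraph and no new data. The cost is a smaller exploratory set, with lower power under some patterns, and an estimand conditional on a post-randomisation state.
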